9.0 Safety Assessments and Procedures

Dosing Safety

First dose monitoring

- The first dose of study medication will be administered at the CRC
- All subjects will be placed on continuous telemetry during the first 24 (+/- 2) hours following administration of the first dose of study medication
- Blood pressure measurements will be completed hourly during the first 6 hours post initial dose of study medication and every 4 (+/- 1) hours thereafter unless study doctor determines a different schedule based on safety.

Second dose monitoring

- For subjects who require pharmacologic intervention for symptomatic bradycardia at any time within the first 24 (+/-2) hours, whose electrocardiogram shows new onset second degree or higher AV block at any time within the first 24 (+/-2) hours or who continue to have bradycardia (resting heart rate < 50 beats per min) after 24 (+/- 2) hours (with or without pharmacologic intervention), first dose monitoring procedures will be reinstated following the second dose

Ophthalmologic Examination

Ophthalmologic examination will be performed before initiating study medication and at 4 (+/-1) months after treatment initiation. For subjects who report visual changes, an additional examination will be completed

Vitals

Vital signs will be assessed at study visits per Study Procedures Table (Attachment 1). Blood pressure, heart rate, and oxygen saturation will be taken in a seated position after a rest period of five minutes. Oxygen saturation will be taken via a finger mounted pulse oximeter.

Medical History

The subject's lifetime medical history will be taken during the screening period. Medical history includes previous and current diseases.

Physical Examination

A physical examination including a neurological examination.

Electrocardiograph (ECG)

A supine, 12 lead ECG will be performed according to the Study Procedures Table (Attachment 1). ECGs will be interpreted by a local cardiologist.

Telemetry

Cardiac telemetry, monitoring of the cardiac rhythm and transmission of signals or data from one electronic unit to another by radio waves using a device that provides real-time measurement of a subject's ECG for various lengths of time, will be performed according to the Study Procedures Table (Attachment 1). Subjects will be outfitted with measuring, recording, and transmitting devices. An alerting function will alert CRC staff if the subject is suffering from an acute condition.

Other Safety Assessments

- Unexplained dyspnea has been reported in clinical trials of this study medication; therefore, subjects who develop unexplained dyspnea during the study will complete an assessment of pulmonary function (spirometric testing) and assessment of diffusion lung capacity for carbon monoxide (DLCO).
- Subjects will be assessed for active infectious disease by clinical history (and physical exam, if necessary) at each study visit.
- Liver enzymes will be monitored at baseline (Visit 1), 4 weeks (Visit 7), and 8 weeks (Visit 11) as well as at the two month follow up visit (Visit 13) and in subjects who develop signs or symptoms of liver dysfunction including unexplained nausea and/or vomiting, abdominal pain, fatigue, anorexia, jaundice, and/or dark urine.

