Fingolimod also causes a dose-dependent reduction in peripheral lymphocyte count to 20%-30% of baseline values because of reversible sequestration of lymphocytes in lymphoid tissues. Fingolimod may therefore increase the risk of infections, some serious in nature. Additionally, in clinical trials there have been rare cases of posterior reversible encephalopathy syndrome (PRES) reported in patients receiving fingolimod. Dyspnea was reported in 9% of patients receiving fingolimod 0.5 mg and 7% of patients receiving placebo in MS placebo-controlled trials. Also, in 2-year placebo-controlled clinical trials, elevation of liver transaminases to 3-fold the upper limit of normal (ULN) or greater occurred in 14% of patients treated with fingolimod 0.5 mg and 3% of patients on placebo. Elevations 5-fold the ULN or greater occurred in 4.5% of patients on fingolimod and 1% of patients on placebo. Based on animal studies, fingolimod may cause fetal harm. Fingolimod also increases the risk of macular edema, the risk of which is increased in patients with a history of uveitis and patients with diabetes mellitus. In 2-year, double-blind, placebo-controlled studies in patients with multiple sclerosis, macular edema with or without visual symptoms occurred in 1.5% of patients (11/799) treated with fingolimod 1.25 mg, 0.5% of patients (4/783) treated with fingolimod 0.5 mg and 0.4% of patients (3/773) treated with placebo.

Rationale of Study Period

Two months was chosen as the treatment period because it is an adequate duration for an initial safety assessment in schizophrenia of early emerging adverse events. In addition, significant effects in MS patients were observed as early as two months post randomization (16). Further, Garver et al (25) reported improvement in DTI-determined white matter integrity in patients with schizophrenia who responded to antipsychotic drug therapy in only 28 days. Thus, if fingolimod has a large effect in improving the symptoms of schizophrenia, it may be detected in a two month study of 40 subjects.

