4.0 Study Design

This will be a single site safety and proof of concept study conducted at the Indiana University Psychotic Disorders Program. Forty subjects with schizophrenia or schizoaffective disorders with suboptimally treated symptoms (despite previous and/or current antipsychotic medication exposure) (39) will be randomized 1:1 to double-blind treatment with fingolimod or matched placebo for duration of 8 weeks.

All subjects will be admitted to the Indiana Clinical and Translational Sciences Institute Clinical Research Center (CRC) and remain hospitalized for the first 24 (+/- 2) hours post initial dose of study medication. The CRC is located in Indiana University Hospital and has 24 hour staffing with nurses skilled in conducting Phase 1 and Phase 2 investigational drug studies.

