10.0 Criteria for Rescreening, Repeat Assessments, and Discontinuation

Repeat Assessments

Screening assessments can be repeated within the screening window under the same screening number with the exception of eligibility criteria related rating scales/questionnaires. Subject diagnosis confirmation will not be repeated.

Rescreening

Subject who screen fail may be rescreened one time, under a new screening number. If a subject is rescreened, all screening assessments (with the exception of the diagnosis confirmation) must be repeated and the stability criteria timelines must be met.

Discontinuation

Subjects will be discontinued under the following circumstances:

1. Within the first two weeks of treatment, subjects with an interruption of treatment of one day or more
2. Within the third and fourth week of treatment, subjects with an interruption of treatment of more than seven days
3. Subjects who have an elevation of liver transaminase levels >3 times the ULN while on study medication
4. Subjects who develop moderate or severe renal impairment as defined by CrCl <60 ml/min (measured by the Cockcroft-Gault equation) while on study medication
5. Female subjects who become pregnant while on study medication
6. Subjects who develop a serious infectious disease while on study medication
7. Subjects who develop macular edema or uveitis while on study medication
8. Any subject who requires pharmacologic intervention for symptomatic bradycardia after the second dose of study medication or who continues to experience bradycardia or who demonstrates any other new, serious cardiac pathology 24 (+/-2) hours after the second dose of study medication will be discontinued from the study
9. Subjects who require an increase in their dose of antipsychotic medication or the addition of a new antipsychotic medication
10. Subjects who require treatment with any excluded concomitant medications (See Attachment 2)

If subjects discontinue from the study, discontinuation assessments will be at the discretion of the principal investigator.

A subject may withdraw from the study medication at any time at his/her own request, or may be withdrawn at any time at the discretion of the principal investigator for safety, behavioral, or administrative reasons.

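### Does the absence of a scheduled eye examination during the 8 weeks of dosing require a change to the plan?

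*Combined protocol and SAP*

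**What the plan says.** Section 4.0 sets "double-blind treatment with fingolimod or matched placebo for duration of 8 weeks", so dosing ends at nominal Day 56 (Visit 11/ET in Attachment 1).

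On eye examinations, Section 9.0 has two sentences. The first fixes the routine ones: "Ophthalmologic examination will be performed before initiating study medication and at 4 (+/-1) months after treatment initiation". The second adds a trigger: "For subjects who report visual changes, an additional examination will be completed". The Ophthalmology Exam row of Attachment 1 has marks at Visit 1b (screening) and Visit 13 (Day 112) and nowhere else. Elsewhere in Section 9.0, Visit 13 is described as the two-month follow-up.

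Section 10.0, item 7, requires discontinuation of "Subjects who develop macular edema or uveitis while on study medication". The same section adds: "If subjects discontinue from the study, discontinuation assessments will be at the discretion of the principal investigator".

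Section 2.0 lists macular edema among the most serious side effects and gives 2-year rates from MS studies: "macular edema with or without visual symptoms occurred in 1.5% of patients (11/799) treated with fingolimod 1.25 mg", then "0.5% of patients (4/783) treated with fingolimod 0.5 mg and 0.4% of patients (3/773) treated with placebo". Section 12.0 sets the trial dose at 0.5 mg daily.

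**The concern.** Safety is the first primary aim (Section 3.0), and Section 2.0 counts macular edema with or without visual symptoms. Yet during dosing the only planned route to a diagnosis starts with the subject reporting a visual change. Some neighbouring discontinuation items have routine on-treatment checks behind them, such as liver enzymes at Visits 7 and 11 and repeated urine pregnancy tests. Item 7 has none.

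Three consequences seem to follow:

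- A subject with symptom-free edema could complete dosing with the protocol followed to the letter, although item 7 calls for discontinuation.
- A case found at Visit 13 could not be dated to on or off drug, and a symptom-free case that had cleared by then would not be seen.
- No eye examination is marked at Visit 11/ET and discontinuation assessments are discretionary, so the text does not say whether an early stopper has any post-baseline examination.

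A report of no macular edema would then mean only that no symptomatic case arose on treatment and that no case was present at Visit 13 among those examined.

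**Working it through.** **Step 1: can any visit window bring the second examination inside dosing?** Inputs are the Attachment 1 windows (days since the last visit) and footnote d.

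- Visit 11 is the eighth visit after first dose (Visits 4 to 11), each 5 to 9 days after the one before: 8 × 5 = Day 40 to 8 × 9 = Day 72. If Visit 11 is split over 7 days, the latest is 72 + 7 = Day 79.
- Visits 12 and 13 are each 24 to 32 days after the one before, so Visit 13 is 48 to 64 days after Visit 11. The earliest possible is 40 + 48 = Day 88.
- The Section 9.0 window of 3 to 5 months opens at 3 × 30.44 = Day 91, or 3 × 28 = Day 84 with four-week months.
- Nominally, Day 112 is 112/30.44 = 3.7 months, inside the stated window and 112 − 56 = 56 days after dosing ends.

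No allowed window puts a routine post-baseline examination within dosing. The factual part of the concern holds.

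**Step 2: do the passages contradict each other?** Section 9.0 (4 ± 1 months) and Attachment 1 (Day 112) agree. Item 7 is conditional: it states the consequence of a finding, not how often to look. It has a working input, the examination for reported visual changes, supported by adverse-event collection at visits. Item 6 (serious infection) works similarly, through clinical history at each visit with physical examination only if needed. A rule fed by a symptom trigger is coherent.

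**Step 3: how many cases are at stake?** First, the plan's rates: 4/783 = 0.51% and 3/773 = 0.39%, matching the printed 0.5% and 0.4%. (11/799 is 1.38%, not the printed 1.5%, but that is the 1.25 mg dose and is not used here.) With 40 subjects randomized 1:1, 20 receive fingolimod.

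| Quantity | Full 2-year risk | Prorated to 8 weeks (× 8/104) |
|---|---|---|
| Fingolimod 0.5 mg: 20 × 4/783 | 0.102 | 0.0079 |
| Placebo rate: 20 × 3/773 | 0.078 | 0.0060 |
| Excess | 0.025 | 0.0019 |

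Prorating assumes a constant rate. The documents do not give time to onset, so the first column is the upper extreme, with all of the 2-year risk falling in the first 8 weeks. At the constant rate, one case is expected per 1/0.0079 ≈ 127 trials of this size, and one excess case per 1/0.0019 ≈ 530.

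These counts include symptomatic cases, for which Section 9.0 already provides an examination. The documents do not say how many of the 4 cases were symptom-free, so the number at issue lies between zero and the figures shown.

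**Step 4: would different timing sharpen the safety conclusion?** With 0 cases in 20, the one-sided 95% upper bound is 1 − 0.05^(1/20) = 0.139, about 14%, whenever the examination is done. Moving the single examination to Visit 11 would help to date a case, but dosing ends at that visit, so item 7 still could not act. Cases emerging afterwards would then depend on symptom report.

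**The case for a change.** The strongest case for a change does not rest on event counts. A protocol that names an event among its most serious risks, writes a stopping rule for it and acknowledges symptom-free cases should either look for it during dosing or say that it does not. Two or three sentences would do that without any new procedure. The MS rates are also only a guide in this population: Section 2.0 says diabetes raises the risk, and Section 5.0 excludes only inadequately controlled diabetes.

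Part of this stands. No planned procedure would find symptom-free edema before dosing ends, and a reader of the results should know that. The rates are indeed borrowed from another disease.

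The step to a change does not stand. The added sentences would restate what Section 9.0 and Attachment 1 already show, or qualify a conclusion about macular edema that Section 16.0 never plans to draw. The existing timing also has a visible logic. Section 5.0 treats the two months after stopping as still relevant to contraception, tonic water, pregnancy and live vaccines, and an examination at Day 112 falls at the end of that period, where it can find persistent or late cases.

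The early-stopper point is the most useful remnant, but it is small. Section 9.0 ties the examination to the start of treatment and does not restrict it to completers. The discretion in Section 10.0 concerns assessments at discontinuation and need not override that.

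**Conclusion.** The observation is accurate, but it does not call for a change. The schedule is internally consistent, item 7 has a working trigger, and the position of the one post-baseline examination is a trade-off between dating on-treatment cases and finding persistent or late ones. That clinical choice belongs to the investigators, and no particular timing is recommended here.

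The expected number of on-treatment cases among 20 fingolimod subjects is about 0.008 at a constant rate and 0.10 at the extreme. Symptom-free cases are some unknown part of that. These figures assume that the MS rate at 0.5 mg carries over to this population, which the documents cannot confirm. Even a several-fold higher constant rate would leave the expected count well below one.

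What remains is ordinary reporting practice: give the number with a post-baseline eye examination in each arm, including early stoppers, and describe the macular edema result by when and how subjects were examined.

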10.0 Criteria for Rescreening, Repeat Assessments, and Discontinuation

Repeat Assessments

Screening assessments can be repeated within the screening window under the same screening number with the exception of eligibility criteria related rating scales/questionnaires. Subject diagnosis confirmation will not be repeated.

Rescreening

Subject who screen fail may be rescreened one time, under a new screening number. If a subject is rescreened, all screening assessments (with the exception of the diagnosis confirmation) must be repeated and the stability criteria timelines must be met.

Discontinuation

Subjects will be discontinued under the following circumstances:

1. Within the first two weeks of treatment, subjects with an interruption of treatment of one day or more
2. Within the third and fourth week of treatment, subjects with an interruption of treatment of more than seven days
3. Subjects who have an elevation of liver transaminase levels >3 times the ULN while on study medication
4. Subjects who develop moderate or severe renal impairment as defined by CrCl <60 ml/min (measured by the Cockcroft-Gault equation) while on study medication
5. Female subjects who become pregnant while on study medication
6. Subjects who develop a serious infectious disease while on study medication
7. Subjects who develop macular edema or uveitis while on study medication
8. Any subject who requires pharmacologic intervention for symptomatic bradycardia after the second dose of study medication or who continues to experience bradycardia or who demonstrates any other new, serious cardiac pathology 24 (+/-2) hours after the second dose of study medication will be discontinued from the study
9. Subjects who require an increase in their dose of antipsychotic medication or the addition of a new antipsychotic medication
10. Subjects who require treatment with any excluded concomitant medications (See Attachment 2)

If subjects discontinue from the study, discontinuation assessments will be at the discretion of the principal investigator.

A subject may withdraw from the study medication at any time at his/her own request, or may be withdrawn at any time at the discretion of the principal investigator for safety, behavioral, or administrative reasons.

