Med/Psych/ Medication History	X															
Demographics	X															
Physical Exam	X															
Vitals	X			X			X	X	X	X	X	X	X	X	X	X
Ophthalmology Exam		X														X
ECG (triplicate, 1 min apart)	X			X			X	X	X	X	X	X	X	X	X	X
CGI-S&I^e	X			X			X	X	X	X	X	X	X	X	X	X
BPRS	X															
PANSS			X				X			X				X		
PSP			X				X	X	X	X	X	X	X	X	X	X
EQ-5D & Quality of Life			X							X				X		
BACS/Trails B			X							X				X		
MRI			X											X		
BFCRS				X										X		
AIMS					X									X		
SAS					X									X		
BARS					X									X		

Visit	1a	1b	2	3a Inpatient	3b ^a Inpatient	3c ^b Inpatient	4	5	6	7	8	9	10	11 ^d /ET	12	13
Day				-1 to -6 hours	0	1	7	14	21	28	35	42	49	56	84	112
Visit Window (days since last visit) ^f			0-30	0-7	NA	NA	5-9	5-9	5-9	5-9	5-9	5-9	5-9	5-9	24-32	24-32
CBC w/ diff	X									X				X		X
CMP	X									X				X		X
TSH	X															
Beta HCG	X															
VZV Titer	X															
HIV test	X															
Hepatitis Panel	X															
Plasma Cytokines				X							X			X		
Magnesium & Calcium	X															
Lipid Panel	X															
HgbA1c	X															
Urine Toxicology	X		X	X				X	X	X	X	X	X	X		
Urine Pregnancy Test	X		X	X				X	X	X	X	X	X	X	X	X
Adverse Event	X		X	X	X			X	X	X	X	X	X	X	X	X
Concomitant Medication	X		X	X	X			X	X	X	X	X	X	X	X	X
Medication Dispensation					X ^c	X		X	X	X	X	X	X	X		
Medication Accountability								X	X	X	X	X	X	X		
Telemetry						X	X									
Hourly Blood Pressure					X	X										

a 3b is the first 24 +/- 2 hours post dose

b 3c will be completed per dosing safety section as outlined in this protocol (if applicable)

c Initial dose will be administered before 12pm

d Visit 11 procedures may be split over a 7 day period

e Only CGI-S will be completed at visit 1a

f: All visits may be split at the discretion of the principal investigator

ATTACHMENT 2

Concomitant Medication Table

Medication	Use prior to Visit 4	Use after Visit 4
Class 1a antiarrhythmic	No	No
Class 3 antiarrhythmic	No	No
Alpha 2 agonists (eg., Clonidine)	No	No
Alpha-adrenergic blockers (eg., doxazosin, terazosin)	Stable dose, no changes or additions	Stable dose, no changes or additions
Anticoagulants	No	No
Antiemetics (eg., metoclopramide, domperidone, other dopamine receptor blockers)	No	No
Antiepileptic mood stabilizers	Stable dose, no changes or additions	Stable dose, no changes or additions
Antihistamines, nonsedating	Yes	Yes
Antihistamines, sedating	Yes ^a	Yes ^a
Antineoplastics	No	No

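### Mandatory interruption limits end at week 4 of 8, so a gap of any length in weeks 5-8 can be followed by a restart with no required monitoring

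*Combined protocol and SAP*

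**What the plan says.** **Treatment length.** Section 4.0 states that subjects "will be randomized 1:1 to double-blind treatment with fingolimod or matched placebo for duration of 8 weeks".

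**Interruption limits.** Section 10.0 lists circumstances in which a subject must be discontinued. Item 1 reads: "Within the first two weeks of treatment, subjects with an interruption of treatment of one day or more". Item 2 reads: "Within the third and fourth week of treatment, subjects with an interruption of treatment of more than seven days". Items 3 to 10 turn on other events: liver enzymes, renal function, pregnancy, infection, eye findings, cardiac findings, antipsychotic changes and excluded medication. The investigator may also withdraw a subject for safety at any time.

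**Monitoring.** Section 9.0 ties intensive observation to the start of treatment: "The first dose of study medication will be administered at the CRC", and "All subjects will be placed on continuous telemetry during the first 24 (+/- 2) hours following administration of the first dose of study medication". For subjects with specified bradycardia or AV-block findings in that period, "first dose monitoring procedures will be reinstated following the second dose". Attachment 1 provides for that repeat as Visit 3c on Day 1, with the footnote "3c will be completed per dosing safety section as outlined in this protocol (if applicable".

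**Other controls.** Attachment 1 schedules vital signs and an ECG ("ECG (triplicate, 1 min apart") at each weekly visit from Visit 4. Section 12.0 adds questioning and a medication count at each visit, and refers to the package insert for more on dosing.

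**The concern.** The plan treats interruption as a safety matter serious enough for mandatory withdrawal, then stops doing so halfway through treatment. A subject who misses eight days in week 3 must stop. One who misses eight days, or far more, from week 5 onward may resume at home with no required observation.

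Safety is the first primary aim in Section 3.0. The plan's caution about cardiac effects is plain: 24 (+/- 2) hours of inpatient telemetry after the first dose, exclusion of conduction disorders, and exclusion of beta blockers and similar drugs. Section 2.0 places the largest fall in heart rate six hours after the initial dose. If any of that effect came back on re-exposure, a routine ECG on a later day would not be timed to catch it.

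There is also a practical problem. Site staff have no rule for a gap that begins in week 4 and continues into week 5, so two subjects with the same gap could be handled differently.

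**Working it through.** The plan states no figure on this point, so the check applies the rules as written to specific gaps.

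**Inputs**
- Treatment: 8 weeks (Section 4.0). Counting the first dose as Day 0, doses fall on Days 0-55.
- Weeks 1-2 are Days 0-13, weeks 3-4 are Days 14-27, and weeks 5-8 are Days 28-55.
- Item 1: a gap of 1 day or more in weeks 1-2. Item 2: a gap of more than 7 days in weeks 3-4 (Section 10.0).
- Nominal visits from week 5: Days 28, 35, 42, 49 and 56, with 5 to 9 days allowed between visits (Attachment 1).

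**Step 1: the same gap, early and late**
- Days 14-21 missed: 21 - 14 + 1 = 8 days, all in weeks 3-4. 8 > 7, so item 2 requires discontinuation.
- Days 28-35 missed: 35 - 28 + 1 = 8 days, all in weeks 5-8. No item applies, and dosing can resume on Day 36.
- Days 28-54 missed: 54 - 28 + 1 = 27 days. No item applies, and dosing can resume on Day 55. This is the longest gap within weeks 5-8 that still leaves a restart dose.

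**Step 2: a gap that crosses week 4/5**
- For a gap of eight days or more starting on Day g, with g from 21 to 27, the days falling in weeks 3-4 number 28 - g, which is 7, 6, 5, 4, 3, 2 or 1.
- If only days in weeks 3-4 count, none of these exceeds 7 and item 2 never applies. If the whole gap counts, item 2 applies to all of them.
- Example: Days 24-31 missed is 8 days in total, 4 of them in week 4. The two readings give opposite instructions.

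**Step 3: is a monitored restart required anywhere?**
- Section 9.0, first dose: tied to the first administration.
- Section 9.0, second dose: conditional on findings in the first 24 (+/- 2) hours.
- Attachment 1: the only repeat-monitoring visit is 3c, on Day 1.
- Section 10.0, item 8: acts on cardiac findings related to the second dose; it schedules no observation for a later restart.
- Nothing addresses a restart after a gap.

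**Step 4: what the remaining controls do**
- ECG: in the Step 1 example, a restart on Day 36 comes one day after the Day 35 visit. The next nominal ECG is on Day 42, 42 - 36 = 6 days later, against a heart-rate low that Section 2.0 puts at six hours after the initial dose.
- Medication count: on the nominal calendar, an eight-day gap always includes a visit, so staff would usually see it. With visits nine days apart (say Days 35 and 44), the eight days 36-43 fall between them. Either way, no action is tied to the finding.

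**The case against.** The strongest reply is that the looser late rule is deliberate. The limits relax with time on drug, and Section 2.0 says heart rate returns to normal within a month of treatment, which matches the week-4 cut-off. This stands in part. It makes a limit longer than seven days plausible for weeks 5-8, and nothing in the documents supports seven days there. But the statement describes patients on treatment, not re-exposure after a long gap, and the same sentence mentions delayed cardiac effects. It does not explain having no limit at all.

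Second, there are real safeguards: weekly ECG and vital signs, medication counts, investigator discretion, and the package-insert reference in Section 12.0. These lower the concern. None sets a limit or covers the restart dose. The insert is not among the documents, so its content cannot be checked, and a general reference in the dosing text is not a protocol rule.

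Third, a reader might infer that a restart is known to bring back first-dose bradycardia, so that subjects would face an established hazard. The documents do not say this. Section 2.0 describes effects after the initial dose only and is silent on whether they return, or after how long off drug.

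Fourth, a reader might take the uncovered half of the treatment calendar (28 of 56 days) as a measure of risk. It is not. It counts days, and says nothing about how often gaps occur or what follows them.

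**Conclusion.** The gap in the rules is real and should be closed. The mandatory limits cover weeks 1-4 only, restart monitoring is not required anywhere, and gaps crossing week 4/5 can be read two ways. As written, up to 27 consecutive missed days in weeks 5-8 can be followed by an unmonitored restart without breaching the protocol.

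The size of the resulting risk is unknown. It depends on the interruption rate and on whether first-dose effects return, and the documents give neither. Only subjects on fingolimod, nominally 20 of 40, could be affected pharmacologically.

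The conclusion assumes that Section 10.0 is read literally and that the package insert is not treated as binding protocol text. It is a safety-conduct point: no power figure or efficacy conclusion changes. It does not show that subjects would be harmed, or that seven days is the correct late limit.

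**What to change.** Add one item to Section 10.0 with four parts:

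1. **Limit.** Set a maximum number of consecutive missed days for weeks 5-8. The clinical team chooses the number from the package insert that Section 12.0 already cites. If no other number can be justified, more than seven days, carried over from item 2, is a conservative fallback and should be labelled as such.
2. **Counting.** When a gap crosses from week 4 into week 5, count the whole run of missed days.
3. **Above the limit.** The subject does not resume study drug but stays in scheduled follow-up, including the week-8 PANSS and safety assessments. This must be explicit, because Section 10.0 leaves assessments after discontinuation to the investigator and week-8 data could otherwise be lost.
4. **Alternative.** If the sponsor prefers to allow a restart, it takes place only under the Section 9.0 first-dose monitoring, with an optional visit added to Attachment 1.

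The cost is a few sentences and, if restarts are allowed, one optional row or visit in the schedule. The downside is that an occasional late interrupter stops drug or repeats one monitored dose of about 24 hours.
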